### **9.3.2.3 Positive and Negative Affect Schedule**

The Positive and Negative Affect Schedule (Watson, Clark and Tellegen, 1988) consists of 20 adjectives describing feelings or emotions (e.g., excited, scared, irritable, nervous). Respondents rate the extent to which they feel each of the 20 adjectives. A 5-point scale includes options ranging from "Very Slightly or Not at All, to Extremely." The 20 adjectives can be rated in approximately 10 minutes. The instrument can be administered using a variety of different temporal options ranging from *right now* to *generally*, permitting the feelings and emotions to be assessed as a characteristic *trait*, or a current *state* of mind. Treatment benefits are likely to

effect changes in an individual's state. Trait findings, however, are not typically sensitive to treatment effects. To elucidate further the relation between reports of tinnitus distress and reports of depressive symptoms, it is helpful to determine whether negative affect is characteristic of the individual in general, or if the negativity is a current state related to events that are impacting him or her now.

In the TRTT, the Positive and Negative Affect Schedule will be used to rate how much each Study Participants generally believes each of the adjectives apply to him or herself, and will be administered at baseline, and at the 6 and 18 months Follow-up Visits.

#### **9.3.2.4 Life Events Checklist**

The instrument used to assess well-being in the TRTT is the Life Events Checklist. Life events can result in stress and anxiety that impact well-being in a number of ways that can ultimately affect or confound treatment efficacy and success. In the TRTT we will use the Life Events Checklist (LEC, Kricos, Erdman, Bratt, and Williams, 2005). The LEC is based on the content of the 43-item Social Readjustment Rating Scale (Holmes and Rahe, 1967; Miller and Rahe, 1997) and the 90-item Life Events Inventory (Cochrane and Robertson, 1973). It was originally developed for use in the National Institute of Deafness, and Other Communication Disorders/Veterans Administration Hearing Aid Clinical Trial to identify life events that could interfere with adjustment to hearing problems and/or hearing aid use. The content of the parent instruments were reviewed by a panel of VA and consulting audiologists and consolidated into 13 items by combining related content areas. The Life Events Checklist can be completed in 5-20 minutes depending on the extent to which a patient chooses to describe the impact of the intervening life event on his or her tinnitus.

The Life Events Checklist will be administered at entry into the TRTT and again at the 6 and 18 month Follow-up Visits to monitor significant changes in an individual's life that could contribute to or confound tinnitus distress or benefit from treatment.

#### **9.3.4 Digit Symbol Substitution Task**

The Digit Symbol Substitution Task is a test of cognitive function that assess the ability of an individual to focus attention to a task and recall. It consists of digit-symbols pairs followed by a series of digits with blanks below. The respondents are required to write in the symbol that is paired with the digit in the blank space as quickly as possible within the allocated time, usually 90 seconds. In the TRTT, we will use the Digit Symbol Substitution Task to assess the ability of the Study Participant to concentrate. Indirectly, this measure will assess the ability of the Study Participant to ignore the tinnitus signal to complete a task requiring attention and psychomotor

skill. Strictly speaking, the Digit Symbol Substitution Task is not a self-report instrument, but will be administered by the Clinical Coordinator or Study Audiologist at baseline, and at the 6 and 18 month visits.

### **9.3.5 Other Quality of Life Measures**

#### **9.3.5.1 Hearing Handicap Inventory**

The Hearing Handicap Inventory for Adults (Newman, Weinstein, Jacobsen, and Hug, 1990) is a 25-item self-assessment scale that measures the impact of hearing impairment on communication ability in daily life and assesses two subscales (emotional and social/situational). A screening version was derived from the original Hearing Handicap Inventory for Adults with only 10 items and similar psychometric properties and with 5 items contributing to each subscale (Newman, Weinstein, Jacobsen and Hug, 1991).

In the TRTT, the Hearing Handicap Inventory for Adults screen will be used to assess how much the impact of hearing loss will affect the overall and tinnitus related quality of life for Study Participants with mild hearing impairment. The Hearing Handicap Inventory for Adult Screening version will be administered at Baseline and then again at the 6- and 18-month Follow-up Visits.

#### **9.3.5.2 EuroQOL**

The EuroQOL is an instrument used to assess general health-related quality of life. It consists of 5 items assessing difficulty in performing activities of daily living using a three part Likert scale assessing degree of ability to perform the task (none, some, or cannot perform). The EuroQOL also has a visual analogue scale, which is a 20 cm scale with an endpoint at the top labeled as best imaginable health state and a score of 100 and an endpoint at the bottom labeled worst imaginable health with a score of 0. The EuroQOL is widely used as a measure to assess overall health benefit of an intervention for determination of cost-benefit analyses. In this setting, the instrument is used to compare the effectiveness of an intervention compared with other health conditions.

The EuroQOL will be administered at entry into the TRTT and again at the 6 and 18 months Follow-up Visits to assess change in general health related quality of life.

---

---

**Table 1**  
**Sequence of Administration of Self-Report Instruments**

---

The self-report and cognitive instruments will be administered in the same sequence for all Study Participants. The test order for baseline and follow-up visits is as follows:

**Baseline Visit: during baseline visit to assess eligibility**

1. Tinnitus Questionnaire
2. Beck Depression Inventory Fast Screen

**Randomization Visit: after patient has signed informed consent, but before randomization takes place (in this order)**

1. Tinnitus Functional Index
2. Tinnitus Handicap Inventory
3. Digit-Symbol Substitution Task
4. Hearing Handicap Inventory
5. State-Trait Anxiety Inventory
6. Positive and Negative Affect Schedule
7. Life Events Checklist
8. EuroQOL

**3 and 12 month Follow-up Visits**

1. Tinnitus Questionnaire
2. Tinnitus Functional Index
3. Tinnitus Handicap Inventory
4. Beck Depression Inventory Fast Screen

**6 and 18 month Follow-up Visits**

1. Tinnitus Questionnaire
2. Tinnitus Functional Index
3. Tinnitus Handicap Inventory
4. Beck Depression Inventory Fast Screen
5. Digit-Symbol Substitution Task
6. Hearing Handicap Inventory
7. State-Trait Anxiety Inventory
8. Positive and Negative Affect Schedule
9. Life Events Checklist
10. EuroQOL

**30, 42, and 54 month Follow-up Visits (annual visits until study close-out)**

1. Tinnitus Questionnaire
2. Tinnitus Functional Index
3. Tinnitus Handicap Inventory

#### **10.1 Introduction**

Each randomized participant enrolled into the Tinnitus Retraining Treatment Trial (TRTT) is seen for the following visits: Baseline Eligibility Visit, Randomization Visit, two Treatment Visits, and Follow-up Visits at 3 months, 6 months, 12 months, and 18 months after the first Treatment Visits, and annually thereafter until study close-out. Additional clinic visits to provide patient care may be scheduled as needed, but such visits are at the discretion of the Study Audiologist or request by the Study Participant. Any pertinent information collected at these additional visits is recorded on an Unscheduled Contact Form. The regularly scheduled study visits are listed in Table 10.1.

Information for the specific study visits is provided in the following sections: Baseline Eligibility Visit and Randomization Visit (Chapter 5), Treatment Administration, Sections 10.2; Follow-up Visits, Section 10.3 and 10.4. Procedures for handling missed visits, inactive Study Participants, transfer Study Participants, deceased Study Participants, and other special problems in follow-up are found in Sections 10.4 through 10.8.

## **10.2 Treatment Administration**

The Initial Treatment Visit (T1) may take place immediately following the Randomization Visit, but must take place within two months following the Randomization Visit. If, for any reason, T1 cannot take place within two months, then an application may be made to the Steering Committee to extend the time window.

T1 will include directive counseling (DC) or the standard of care (SC) clinical consultation usually provided in the military, according to the treatment assignment. For Study Participants assigned to sound generators (SGs), T1 will also include fitting and activation of these devices. Procedures used to administer these treatments are described in Chapters 11 and 12.

When T1 has been completed and the date of the visit recorded on the TRTT website, an appointment schedule for the Study Participant will be automatically re-generated. The dates specified on this schedule are based on the date of T1. This schedule lists the ideal dates for all succeeding follow-up study visits, with the permissible time window within which each visit must be completed. There will be a data entry slot on the schedule for the Clinical Coordinator to record the actual date of completion of each follow-up visit.

At one month following T1, Study Participants assigned to DC will complete reinforcement counseling. At this time, the proper use, and maintenance of SGs will also be reviewed. This one month follow-up visit is considered part of the Treatment Visit, and is called Treatment Visit 2 (T2). Study Participants assigned to SC will also be seen at T2 to monitor progress and to maintain the same amount of personal contact.

Measurement of loudness discomfort level (LDL) is an important piece of the treatment protocol for all patients and especially for hyperacusis patients. LDL is tested by measuring pure tone thresholds at the frequencies that the LDL is measured, and then by measuring LDL thresholds. The blinded Study Audiologist will measure LDLs at T2 and at the 3 month Follow-Up Visit using the LDL Assessment for Treatment Form. It is also collected during the Baseline and Follow-up ATH exams. The counseling Audiologist is permitted to view this information to use during counseling.

## **10.3 Follow-up Visits**

Follow-up Visits will take place at 3, 6, 12, and 18 months after T1, and then annually until study close-out. Study Participants in all groups are seen at all Follow-up Visits. All Follow-up Visits involve reinforcement counseling as needed.

The Clinical Coordinator or the blinded Study Audiologists (i.e., the Clinical Center Study Audiologist who is not involved in counseling the Study Participant) will complete the Follow-up Medical History Form at each follow-up visit, and ask each participant to complete the following data collection instruments: the Tinnitus Questionnaire, Tinnitus Handicap Inventory, Tinnitus Functional Index, and the Beck Depression Inventory Fast Screen at each Follow-up Visit.

The Follow-up TRT Interview and a full audiological/tinnitus/hyperacusis evaluation, consisting of audiometric pure tone, speech recognition threshold, tinnitus pitch and loudness match, loudness discomfort level (LDL), and word recognition testing will be completed at the 6, 12 and 18 months visit. In addition, the following forms will also be completed at the 6 and 18 month study visits: the Digit Symbol Substitution Test, Hearing Handicap Inventory, State Trait Anxiety Inventory, Positive and Negative Affect Schedule Life Events Checklist, and EuroQOL. It is important that the Study Audiologist who is **not counseling the Study Participant** perform these activities to preserve blinding when measuring these outcomes (see Table 10.2 ).

Note that LDL is checked at all follow up visits. At T2 and the 3 month follow-up visit (F1), the LDL is recorded on the LDL Assessment for Treatment Form for each participant, and at the 6, 12, and 18 months visits, it is recorded on the Audiological/Tinnitus/Hyperacusis (ATH) Examination. LDL testing at these visits is completed by the blinded study Audiologist who is not involved in the treatment of the Study Participant, but the counseling Audiologist may use the LDL results for treatment.

All follow-up visits past 18 months follow-up include only the tinnitus specific health-related quality of life instruments are collected (i.e, the Tinnitus Questionnaire, Tinnitus Functional Index, and Tinnitus Handicap Inventory). These forms may either be completed in person or mailed and returned by post. An in-person visit is not required.

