#### **2.1 Purpose/Objectives of the Trial**

The primary objective of the Tinnitus Retraining Therapy Trial (TRTT) is to assess the efficacy of Tinnitus Retraining Therapy (TRT) as a treatment for severe debilitating tinnitus. TRT is an habituation-based intervention that uses directive counseling (DC) and low-level sound therapy (ST) to facilitate habituation of the awareness of tinnitus, its annoyance, and impact on the patient's life.

Millions of Americans experience varying levels of distress from tinnitus, but tinnitus is severely disabling for as many as 2-5 million individuals. In the absence of a cure for debilitating tinnitus and with no proven intervention shown conclusively to ameliorate the symptoms or distress caused by tinnitus, TRT has become the therapeutic intervention "of this decade." TRT, however, remains highly controversial and requires validation in a rigorous, controlled clinical trial.

The TRTT is a randomized, double-blind, placebo-controlled, multi-center, clinical trial for individuals with intolerable tinnitus. The TRTT will include persons with functionally adequate hearing sensitivity who do not need to use hearing aids. Eligible Study Participants will be randomized to one of three treatment arms to compare the efficacy of full TRT versus the standard of care in the military (SC). The trial design will also contrast the treatment effects of DC in combination with ST as implemented in TRT with conventional low-level sound

generators (SGs) versus placebo SGs. In addition, the TRTT will evaluate the efficacy of DC by comparing individuals randomized to DC and placebo SGs versus SC.

The TRTT will be conducted at flagship Air Force, Navy, and Army Medical Centers with active-duty and retired military personnel and their dependents. The likely higher incidence of noise-induced tinnitus than in the general population and the great diversity of this study population makes the U.S. Armed Forces an ideal study group for a clinical trial of TRT.

The primary outcome to be measured in the TRTT will be change in scores on the Tinnitus Questionnaire (TQ) longitudinally assessed between baseline and follow-up (i.e., at 3, 6, 12 and 18 months following treatment). Secondary outcomes include change in other tinnitus repeated-measures self-report tinnitus questionnaires, changes in the sub-scales of the TQ, and change in the Digit Symbol Substitution Task (DSST), EuroQOL, and audiological data.

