## **5.5 Participant Randomization Procedures**

Before Randomization takes place, the Clinical Coordinator reviews the current Eligibility Checklist to establish the potential Study Participant's eligibility. He or she confirms that the potential Study Participant has given informed consent as demonstrated by signing the Informed Consent Statement, and that he or she has completed all baseline forms. Finally, the Study staff again explains the study, ensures that the participant truly understands the study, and makes certain that no additional questions or concerns remain. Study staff also ensures that the Study Participant, even if eligible, is still willing to allow randomization to an assigned treatment.

The Clinical Coordinator then accesses the randomization page of the TRTT website to obtain a randomization assignment. Using the internet ensures that 24 hours per day, 7 days a

week central randomization for the TRTT will be available. The Clinical Coordinator first enters the study specific code and the site-specific password that has been provided to the Clinical Center for this purpose. After the system verifies that the investigator is eligible to use the system, he or she enters the Study Participant's ID number and name code. At this time the Clinical Coordinator will be required to enter the qualifying TQ and the Eligibility Checklist. In so doing, the TRTT inclusion and exclusion criteria will be reviewed to ensure that the person to be entered is actually eligible to participate and that informed consent has been obtained. At this time, the system will provide the randomized treatment assignment.

Participants are randomized to one of three treatment groups. The participant has an equal probability of assignment to full TRT (Directive Counseling (DC) and conventional sound generator (SG)); modified TRT (DC and placebo SG); or standard of care (SC) for tinnitus as provided in the military (See Chapter 23 for further details on the statistical design).

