In the trial, randomization will be stratified by Clinical Center. The sequence of random treatment allocations is designed to occur in blocks within each Clinical Center. There are blocks of allocations equal in length to a multiple of the number of treatment groups, i.e. multiples of 3. The exact multiple varies, at random, from block to block to make any particular assignment impossible to predict even if the treatment becomes unblinded. If there is a block of size "n", then at the end of that block, " $n/3$  Study Participants will have been allocated to each of the treatment groups. For example, a block size of 12 assignments for a given clinic will result in exactly 4 Study Participants who are allocated to each of the three treatment groups in a random order. The random order of the allocations for each stratum (clinical center and hearing aid use) is generated using the Moses-Oakford algorithm for computer generation of random permutations.

After the treatment group has been assigned, the system will generate a printable Randomization Registration Report as confirmation of the treatment assignment. The Randomization Registration Report will provide a kit number. The kits are boxes which contain the randomization assignment, either "Directive Counseling and Sound Generator" or "Standard of Care." If assigned to "Directive Counseling and Sound Generator," the kit will also include the pair of sound generators assigned to that Study Participant.

The Study Participant is officially enrolled in the trial at the time the treatment assignment is generated online. Once randomized, the participant **must be included** in the primary analyses of the assigned treatment group regardless of any difficulties that may arise in the treatment or follow-up processes.

Treatment may begin at the Randomization Visit, if time and circumstances allow, or may be scheduled for a future date. The first Treatment Visit (T1) must occur within two months of the Randomization Visit, however. If it cannot be scheduled within two months, an application to the Steering Committee may be made to extend the allowable time window. Chapters 11, 12, and 13 of the TRTT Manual of Procedures describe the administration of the interventions in detail.

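### A Clinical Coordinator who can know sound generator versus standard of care may collect follow-up outcomes, and the unqualified double-blind label does not fit the primary comparison

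*Combined protocol and SAP*

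**What the plan says.** **Who learns the assignment.** Section 5.5: "The Clinical Coordinator then accesses the randomization page of the TRTT website to obtain a randomization assignment". After the eligibility data are entered, "At this time, the system will provide the randomized treatment assignment". The printed report gives a kit number. On the kits the section says "The kits are boxes which contain the randomization assignment", worded either as directive counseling (DC) with a sound generator (SG) or as SC. Conventional and placebo SGs are not distinguished there.

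**Who collects the follow-up outcomes.** Section 10.3 gives the follow-up medical history and four self-report forms to "The Clinical Coordinator or the blinded Study Audiologists (i.e., the Clinical Center Study Audiologist who is not involved in counseling the Study Participant"). That person is to "ask each participant to complete the following data collection instruments: the Tinnitus Questionnaire", the Tinnitus Handicap Inventory, the Tinnitus Functional Index and the Beck Depression Inventory Fast Screen. The next paragraph lists the TRT interview, the audiological/tinnitus/hyperacusis (ATH) evaluation and the 6- and 18-month forms, including the Digit Symbol task. It says the audiologist who is not counseling the participant should do these, in order to protect blinding. Loudness discomfort level (LDL) testing is also given to the blinded audiologist.

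**Who gives the Digit Symbol task.** Section 9.3.4 says it "will be administered by the Clinical Coordinator or Study Audiologist at baseline, and at the 6 and 18 month visits". It sets no blinding condition.

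**How the trial is labeled.** Section 2.1: "The TRTT is a randomized, double-blind, placebo-controlled, multi-center, clinical trial for individuals with intolerable tinnitus". Section 1.6 uses the same description. Section 2.5 (bias control) and section 3.2.4 (device supply) apply double-blind only to sound therapy.

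**The concern.** The primary comparison, TRT versus SC, rests on a self-report scale. Section 1.5.3 names patient expectation as a rival explanation for the apparent success of TRT. Section 1.6 cites the lack of double-blind designs among the faults of earlier studies and promises a trial that answers those criticisms.

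Three features of the text work against that promise:

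- A role that can know the arm may be the one who meets the participant for the primary outcome.
- Two sections disagree on who gives a timed, staff-administered test after randomization.
- The trial-level label claims a safeguard that TRT versus SC does not have.

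The first adds an unblinded contact that could be avoided. The second could lead centers to follow different rules. The third would mislead readers of the results.

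**Working it through.** The plan states no figure on this point, so the check sets the sections side by side.

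**1. Can the Coordinator know the arm?** Yes, for SG versus SC. Section 5.5 has the Coordinator request the assignment, and the system then supplies it. The kit wording draws exactly that distinction. Section 5.5 does not say who opens the kit, and nothing in the available text shows the Coordinator learning conventional versus placebo SG.

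**2. Does the Coordinator have access to outcomes?** Yes, in part.

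| Measure | Collector in 10.3 | Collector elsewhere |
|---|---|---|
| Follow-up history | Coordinator or blinded audiologist | – |
| TQ and three other self-report forms | Coordinator or blinded audiologist | 9.2: completed by the participant |
| Digit Symbol task, 6 and 18 months | Non-counseling audiologist | 9.3.4: Coordinator or any Study Audiologist |
| TRT interview, ATH evaluation | Non-counseling audiologist | – |
| LDL | Blinded audiologist | 10.2: blinded audiologist |

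The third row is a direct conflict. The second leaves the primary outcome less protected than several secondary ones, and no reason is given. The blinding sentence in 10.3 points to Table 10.2, which also lists the TQ. If it is read as reaching back to the TQ, section 10.3 contradicts itself. Either way the text needs editing.

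**3. Is the TQ taken before counseling?** Section 10.3 provides reinforcement counseling as needed at every follow-up visit. Table 1 of Chapter 9 orders the instruments among themselves but not relative to counseling. The available text sets no order.

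**4. Does the label fit each comparison?**

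- Conventional versus placebo SG: yes. Both groups get DC and a device, and sections 2.5 and 3.2.4 describe that masking.
- TRT versus SC (primary, section 2.2.3): no. Under section 10.2 only the SG groups are fitted with devices, so participants know which side they are on.
- DC plus placebo SG versus SC: no, for the same reason.

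**5. Can the bias be sized?** Only as a total, and only under assumptions. Section 2.3 gives no SD. With 76 × 0.9 = 68.4 per arm and α = 0.05/3 (two-sided critical value 2.394), 80% power at 7 points implies SD = 7 / [(2.394 + 0.842) × √(2/68.4)] ≈ 12.65. The standard error at one time point is then 12.65 × √(2/68.4) ≈ 2.16. This SD gives 98.7% power at 10 points, which agrees with the stated power above 95%. For an assumed total bias b, the false-positive rate is Φ(−2.394 + b/2.16) + Φ(−2.394 − b/2.16):

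- b = 0: 1.7%
- b = 2: about 7%
- b = 3: about 16%

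These rates cover bias from every source. The documents give no way to split off the collector's part.

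**The case against.** The strongest reply is that the collector hardly matters for the TQ. Section 9.2 has the participant complete it on paper in a private setting. Under 10.3 the Coordinator only asks for it to be completed and rates nothing. The midpoint telephone calls in 10.5.2 go to all participants, so they are not specific to TRT. This largely stands. The route from the Coordinator's knowledge to a privately completed form is weak, and replacing the Coordinator would not mask TRT versus SC. It does not cover the history, which staff complete, or the Digit Symbol task, which staff administer against the clock.

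A second reply is that sections 2.5 and 3.2.4 already limit double-blind to sound therapy. That shows what was meant, but it leaves the unqualified statements in 1.6 and 2.1 uncorrected.

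A reader might go further and infer three things that the documents do not support:

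- *That outcome assessment as a whole is unblinded.* Section 10.3 keeps the TRT interview, ATH evaluation and LDL with the non-counseling or blinded audiologist, and directs the Digit Symbol task there too.
- *That Coordinator collection raises the false-positive rate to 7–16%.* Those rates assume a total bias of 2 to 3 points, use a back-calculated SD, and apply to a single time point although the primary analysis is longitudinal. A change of collector would not remove most of such a bias.
- *That the placebo comparison is compromised.* Nothing shows the Coordinator learning which type of SG was supplied.

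**Conclusion.** The point holds in three limited parts.

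1. A role that can know SG versus SC is allowed to collect the history and hand out the TQ and three other questionnaires. This is an avoidable unblinded contact.
2. Sections 9.3.4 and 10.3 conflict on the Digit Symbol task at 6 and 18 months.
3. The unqualified double-blind label in 1.6 and 2.1 is wrong for TRT versus SC, and also for DC plus placebo SG versus SC.

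The label matters most, because it misstates a property of the primary comparison. The main source of expectation bias is the participant's own knowledge, which no change of collector can remove. The collector's share cannot be quantified from the documents, so no figure is attached to it.

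The conclusion rests on Chapters 1 to 10 and the available part of Chapter 11. Chapters 12 to 25, including those on protocol monitoring, Clinical Center operations and statistics, were not available and may contain further masking rules.

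**What to change.** 1. Reconcile 9.3.4 with 10.3 so that only the non-counseling audiologist gives the Digit Symbol task at 6 and 18 months. Baseline can stay as it is, since section 5.4 places that test before the assignment is requested.
2. In 10.3, delete the Clinical Coordinator as an alternative collector, so that the non-counseling audiologist takes the follow-up history and has the TQ and the other questionnaires completed. State that the TQ is completed before any counseling at that visit.
3. In 1.6 and 2.1, limit double-blind to conventional versus placebo SG. State that TRT versus SC and DC plus placebo SG versus SC are open to participants, with a self-reported primary outcome.

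**Cost.** Wording in Chapters 1, 2, 9 and 10, with no change to the analysis or sample size. No new post is needed, because sections 2.2.2 and 3.2.6.2 give each center at least two Study Audiologists. The downside is audiologist time at each follow-up visit: section 9.3.1.1 puts the TQ at about 20 minutes, and the history and three other forms come on top. Where a center has only two audiologists and one is counseling the participant, no backup collector is assured.
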